6.4.5 Study Day 43 (± 3 days) or Early Termination

The following procedures will be performed:

Targeted physical exam

Vital signs including weight

Laboratory Evaluations:

- Serum chemistry
- Hematology
- Fasting glucose
- Fasting blood insulin level
- NT-proBNP and IL-1 α
- Serum for PK, PD, ADA, and possible exploratory analyses
- Serum pregnancy test in WOCBP

AE assessment

Concomitant medication assessment

Overall status

6.4.6 Study Day 76 (± 5 days)

The following procedures will be performed:

Laboratory Evaluations:

- Serum for PK, PD, and ADA

AE assessment

Concomitant medication assessment

Overall status

6.5 Research Specimens

Additional serum samples are taken for *ex vivo* PD assessments. These assessments will be conducted as defined in a separate protocol, whereby the dosed participants of the study will remain anonymous.

Blood for future research will be obtained on those days PK samples are taken. These PK samples and the additional serum samples for any exploratory assessments are mandatory as part of participation in this study. The PK samples, if not required for repeat of PK assessments, may be retained for future exploratory assessments. These stored samples will remain anonymized

and may be used by the Sponsor or its research partners for retesting of planned tests, characterization of TRL345, further analyses to study CMV infections, or clinical laboratory testing to provide additional safety data. No human genetic testing will be performed on these samples. At the conclusion of this study, these samples may be retained in storage by the investigators, Sponsor or its research partners for a period up to 15 years.

7 ADVERSE EVENTS

AEs, including SAEs, will be reported in a manner consistent with the FDA Guidance for Industry and Investigators, “Safety Reporting Requirements for IND and BA/BE Studies,” December 2012

(<http://www.fda.gov/downloads/Drugs/GuidanceComplianceRegulatoryInformation/Guidances/UCM227351.pdf>).

7.1 Reporting Responsibilities

All AEs, including SAEs, will be recorded in the eCRF from start of IP infusion through Study Day 76. It is the responsibility of the Investigator or Sub Investigator(s) to perform assessment of AEs and SAEs at each study visit. Data describing AEs, and SAEs, will be entered in the subject’s medical record and eCRF. SAEs will be reported to the Sponsor as described in [Section 7.6](#).

Subjects who experience AEs, whether serious or not serious, should receive appropriate treatment and medical supervision as clinically indicated. All AEs must be followed until resolution/stabilization or until a time that is mutually agreed upon between the Medical Monitor and the Investigator.

7.2 Definitions

7.2.1 *Adverse Event*

An AE is any untoward medical occurrence in a patient or clinical investigation subject administered a pharmaceutical product and which does not necessarily have a causal relationship with this treatment. An AE can therefore be any unfavorable and unintended sign (including an abnormal laboratory finding), symptom, or disease temporally associated with the use of an IP, whether or not related to the IP.

7.2.2 *Serious Adverse Event*

An AE or suspected adverse reaction is considered “serious” (SAE) if, in the view of either the Investigator or Sponsor, it results in any of the following outcomes:

- Death
- Life-threatening
 - An AE is considered “life-threatening” if, in the view of either the Investigator or Sponsor, its occurrence places the patient or subject at immediate risk of death. It does not include an AE that, had it occurred in a more severe form, might have caused death.
- Inpatient hospitalization or prolongation of existing hospitalization
- A persistent or significant incapacity or substantial disruption of the ability to conduct normal life functions
- A congenital anomaly/birth defect

- Important medical events that may not result in death, be life-threatening, or require hospitalization may be considered serious when, based upon appropriate medical judgment, they may jeopardize the patient or subject and may require medical or surgical intervention to prevent one of the outcomes listed in this definition.
 - Examples of such medical events include allergic bronchospasm requiring intensive treatment in an emergency room (ER) or at home, blood dyscrasias or convulsions that do not result in inpatient hospitalization, or the development of drug dependency or drug abuse.

If it is not certain that an event meets the above definitions of an SAE, contact the Medical Monitor to discuss.

7.2.3 *Relatedness (Causality)*

Causality assessment is required for AEs (and SAEs) that occur during clinical investigations. There is currently no standard international nomenclature to describe the degree of causality or relatedness of an AE with the IP. The following terms will be used during this study:

Likely - Reasons to consider an AE likely related to treatment may include, but are not limited to the following:

- Timing of the event relative to the administration of the IP
- Location of the AE relative to the site of IP administration
- Likelihood based on experience with similar products
- There is a biologically plausible explanation based on the mechanism of action or mode of delivery of the treatment
- The AE is repeated on subsequent treatments
- No other explanation is likely

Unlikely - An AE with no temporal association with the IP but rather related to other etiologies such as concomitant medications or conditions, or subject's known clinical state.

7.2.4 *Severity*

Each sign or symptom reported will be graded according to the [Guidance for Industry: Toxicity Grading Scale for Healthy Adult and Adolescent Volunteers Enrolled in Preventive Vaccine Clinical Trials](https://www.fda.gov/media/73679/download) (<https://www.fda.gov/media/73679/download>).

7.3 **Clinical Laboratory Abnormalities**

Any laboratory abnormality deemed clinically significant by the Investigator should be reported as an AE. A clinically significant abnormality is a confirmed abnormality (by repeat test) that is changed sufficiently from Screening/Baseline so that in the judgment of the Investigator a change in management is warranted. This alteration may include monitoring the laboratory test further, initiating other diagnostic tests or procedures, changing ongoing treatment, or administering new treatment.

Whenever possible, the medical diagnosis rather than a laboratory value (e.g., “anemia” rather than “low Hb”) should be reported as the AE term. Repeated additional tests and/or other

evaluations required to establish the significance and etiology of an abnormal result should be obtained when clinically indicated.

7.4 Physical Exam Abnormalities

Any physical exam abnormality deemed clinically significant by the Investigator at Day 1 should be reported as medical history. Any new physical exam abnormality deemed clinically significant by the Investigator during the study (after Day 1) should be reported as an AE.

7.5 Pregnancy

No dose will be administered to a pregnant subject. All remaining safety assessments should be performed. **All pregnancies that occur – including female partners of male subjects – during the study must be reported to the Sponsor and followed to conclusion. The outcome of each pregnancy must be reported.**

Pregnancy alone is not an AE, nor is an induced elective abortion to terminate a pregnancy without medical reason. However, an induced therapeutic abortion to terminate a pregnancy due to complications or medical reasons must be reported as an SAE. The underlying medical diagnosis for this procedure should be reported as the SAE term. A spontaneous abortion is always considered an SAE.

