Safety: Frequencies and percentages of subjects with AEs and SAEs will be summarized by dose group. Vital signs, ECGs, laboratory evaluations, and physical examination findings will be summarized with descriptive statistics by dose group. Additional serum samples will be taken and stored for possible exploratory analyses that may be necessary to further explore any unexpected safety or tolerability observations.

PK: Individual subject TRL345 serum concentrations and derived PK parameters will be summarized using descriptive statistics.

Immunogenicity: Anti-TRL345 antibodies will be summarized with descriptive statistics by DG.

PD: Serum samples will be taken and evaluated for *ex vivo* PD assessments.

SCHEDULE OF EVENTS

Study Day	Screening	1	2	3	8	15	29	43	76
Study Week					1	2	4	6	11
Window (days)	-8 (+/-6)	-1	0	0	± 1	± 3	± 3	± 3	± 5
Visit Type	A	RU	RU	RU	A	A	A	A	A
Procedure									
Informed Consent	X								
Eligibility	X	X ¹							
Demographics	X								
Medical/Disease History	X								
Complete Physical Exam	X								
Targeted Physical Exam		X ¹	X	X	X	X	X	X	
Vital Signs ²	X	X ³	X	X	X	X	X	X	
Weight	X	X ¹						X	
Height	X								
12-Lead ECG in triplicate ⁴	X	X			X				
Laboratory Tests									
Serum Chemistry ⁵	X	X ¹	X	X	X	X	X	X	
Hematology	X	X ¹	X	X	X	X	X	X	
Amylase, lipase, creatine kinase ⁶		X ¹		X	X	X			
Fasting glucose	X	X ¹		X	X	X	X	X	
HbA1C	X								
Fasting blood insulin level		X ¹		X	X	X	X	X	
Additional serum sample for possible exploratory analyses ⁷		X ¹		X	X	X	X	X	
NT-proBNP, IL-1 α		X ¹		X		X	X	X	
CMV Serology ⁸	X								
Serum Pregnancy Test (WOCBP)	X							X	
HIV, Hepatitis B, C Serology	X								
Urine Drug Test	X								
Randomization		X ¹							
Dosing of IP (TRL345 or placebo)		X							
PK sampling – serum ⁹		X	X	X	X	X	X	X	X
PD sampling – serum ¹⁰		X				X	X	X	X
ADA sampling – serum ¹¹		X ¹			X		X	X	X
Adverse Events		X	X	X	X	X	X	X	X
Concomitant Medications		X ¹	X	X	X	X	X	X	X
Overall Status								X	X

Visit Type: A = ambulant, RU = Research Unit, NA = phone call

- To be performed prior to the administration of IP.
- Vital signs include temperature, blood pressure, and heart rate. Vital signs should be obtained after subject is resting for 5 minutes. The window for all vital signs is ± 10 minutes.
- On Day 1, vital signs will be obtained within 60 minutes prior to dosing, at 15, 30, and 60 minutes (end of the infusion), and 1 hour and 4 hours after the end of the infusion.

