No genotoxicity studies for TRL345 have been performed. Proteins are not typically considered to possess mutagenic potential based upon the inability to cross intact cell membranes, gain access to cytosolic/nuclear compartments, or integrate with or damage host cell DNA and alter host cell genetic material. Furthermore, there are no impurities contained in the final product formulation at levels high enough to be of mutagenic or carcinogenic concern.

No carcinogenicity studies for TRL345 have been performed. However, there was no evidence of abnormal cell proliferation or immunosuppression in cynomolgus monkeys after dosing with TRL345 IV twice weekly up to 150 mg/kg for 28-Days.

No developmental or reproductive toxicity studies with TRL345 have been performed. However, there was no evidence of macro- or microscopic changes in male or female organs from Sprague-Dawley rats dosed with TRL345 IV twice weekly up to 150 mg/kg for 28 days.

No effects attributable to formulated product were noted in Sprague-Dawley rats dosed with TRL345 IV twice weekly up to 150 mg/kg for 28-Days [ITR Study Report # 72460]. Given the excipients of the formulation buffer (i.e., 20 mM Histidine, 150 mM Sodium chloride, at pH 6.0) TRL345 is not expected to be irritating when administered IV.

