4.1 Inclusion Criteria

1. Healthy male and non-pregnant, non-breast-feeding female subjects at between 18 and 65 years of age, inclusive, and representative of the general population
2. Willing and able to provide written informed consent.
3. Availability for the entire duration of the study, and willingness to adhere to protocol requirements
4. In good health, as determined by lack of clinically significant abnormalities in health assessments performed at the Screening Visit, as judged by the Principal Investigator (PI) or as delegated by the PI to a physician or nurse practitioner as sub-investigator.
5. Men and women of child bearing potential (WOCBP) must be willing to practice a highly effective method of contraception that may include, but is not limited to, abstinence, sex only with persons of the same sex, monogamous relationship with vasectomized partner, vasectomy, hysterectomy, bilateral tubal ligation, licensed hormonal methods, or intrauterine device (IUD) for 28 days before Screening and through Day 76. Men must also refrain from donating sperm from Day 1 through Day 76.

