 - Hemoglobin ≤ 128 g/L (males) and ≤ 115 g/L (females), and hematocrit $\leq 37\%$ (males) and $\leq 32.0\%$ for females
11. Positive test results for HIV, Hepatitis B (HBsAg), or Hepatitis C (HCV) at the Screening Visit
12. History of significant drug abuse within one year prior to the Screening Visit and/or ongoing
13. History of significant alcohol abuse within one year prior to the Screening Visit defined as more than fourteen units of alcohol per week [one “unit” is equal to approximately $\frac{1}{2}$ pint [200 mL] of beer, 1 small glass [100 mL] of wine, or 1 measure [25 mL] of spirits)
14. Positive test for drugs of abuse, ETOH and nicotine (cotinine) at the Screening Visit
15. Positive serum beta-human chorionic gonadotropin test for pregnancy, pregnant, or nursing women
16. Unwilling to refrain from donating blood or plasma during the study.
17. Use of any new prescription medication or over-the-counter (OTC) product (including natural food supplements, vitamins, herbs) within 14 days prior to dosing
18. Receipt of any vaccine or booster within 14 days prior to Day 1 or planned vaccination or booster within 4 weeks after IP administration
19. Any planned medical intervention or personal event that might interfere with the ability to comply with the study requirements
20. Is current study site staff paid entirely or partially by the contract for this trial, or staff who are supervised by the PI or sub-PI

21. Receipt of an investigational product, or participation in another trial involving a marketed or investigational drug within 30 days of Day 1, or 5 half-lives of the investigational drug, whichever is longer
22. Any other comorbidity or condition that, in the opinion of the Investigator would make the subject unsuitable for the study or unable to comply with the study requirements

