6.4 On-Study Procedures

6.4.1 Study Day 1

The following procedures will be performed prior to administration of IP:

Reconfirm eligibility

Targeted physical exam

Concomitant medication assessment

Laboratory Evaluations, including:

- Serum chemistry (including hsCRP and LDH)
- Hematology
- Amylase, lipase, and creatine kinase (subjects must refrain from strenuous exercise within 5 days prior to assessment of creatine kinase)
- Fasting glucose
- Fasting blood insulin level
- NT-proBNP and IL-1 α
- Serum for PK, PD, ADA, and possible exploratory analyses (see additional times below for PK and PD)

The following procedures will be performed at the times specified below:

Vital signs within 60 minutes prior to dosing and then at 15, 30, and 60 minutes (end of the infusion), and 1 and 4 hours after the end of the infusion

Serum for PK will be obtained at prior to the start of infusion and then at end of infusion (60 minutes), and 2, 4, 6, 12, 24 (Day 2), and 48 hours (Day 3) after the start of the infusion

Serum for PD will be obtained at prior to start of infusion and then at end of infusion (60 minutes)

12-lead ECGs in triplicate within 4 hours post-completion of infusion (subjects may not use tobacco or nicotine within 4 hours prior to the ECG)

Additionally, the following will be performed:

Randomization of the subject to study/DG

Intravenous dosing of study IP per randomization assignment. A calibrated IV infusion pump will be set to deliver the total volume of IP over a 60-minute period.

Adverse events will be assessed during and after the infusion.

6.4.2 Study Days 2 and 3

The following procedures will be performed:

Targeted physical exam

Vital signs

Laboratory Evaluations, including:

- Serum chemistry
- Hematology
- Amylase, lipase, and creatine kinase (subjects must refrain from strenuous exercise within 5 days prior to assessment of creatine kinase) (Day 3 only)

- Fasting glucose (Day 3 only)
- Fasting blood insulin level (Day 3 only)
- Additional serum sample for possible exploratory analyses (Day 3 only)
- NT-proBNP and IL-1 α (Day 3 only)
- Serum for PK

AE assessment

Concomitant medication assessment

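### No current pregnancy test supports the Day 1 eligibility reconfirmation: the only scheduled pre-dose result is 2 to 14 days old at dosing

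*Protocol*

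**What the plan says.** Section 7.5 of the protocol states: "No dose will be administered to a pregnant subject". Exclusion 15 in Section 4.2 reads "Positive serum beta-human chorionic gonadotropin test for pregnancy, pregnant, or nursing women". Exclusions 3, 11 and 14 each name the Screening Visit as their time point; exclusion 15 names none.

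The Schedule of Events repeats the eligibility check on Day 1 before the infusion, and Section 6.4.1 opens its pre-dose list with "Reconfirm eligibility". That list then itemizes the Day 1 bloods: chemistry with hsCRP and LDH, hematology, amylase, lipase, creatine kinase, fasting glucose and insulin, NT-proBNP, IL-1 alpha, and the PK, PD, ADA and exploratory samples. It contains no pregnancy test.

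The Schedule marks the serum pregnancy test at Screening and Day 43 only. The visit text agrees: the test is in Section 6.2 (Screening) and in Section 6.4.5 (Day 43 or Early Termination), as "Serum pregnancy test in WOCBP", and in no other visit list. The SAP's baseline laboratory entry (Section 8.5, Day -1) covers chemistry and hematology and adds none.

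Inclusion 5 requires highly effective contraception "for 28 days before Screening and through Day 76". Section 1.3.3 records: "No developmental or reproductive toxicity studies with TRL345 have been performed".

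**The concern.** The plan sets an absolute bar and asks for eligibility to be confirmed again just before dosing, but gives the investigator no current measurement for that check. On Day 1 the available evidence is the Screening result, what the subject reports, and her commitment to contraception. None of these establishes her status on the dosing day.

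At stake is exposure of an early pregnancy to an antibody never before given to humans (Section 1.4) and without developmental or reproductive toxicity data. The study gives one infusion, so an error found afterwards cannot be corrected by withholding later doses.

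**Working it through.** The protocol gives no figure of its own for this point. The check is a reading of the Schedule of Events followed by visit-window arithmetic.

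**1. Where the test is scheduled.** The header of the Schedule has nine visit columns: Screening and Days 1, 2, 3, 8, 15, 29, 43 and 76. Matching the pregnancy-test row to these by position gives marks under Screening and Day 43 only. Sections 6.2 and 6.4.1 to 6.4.6 say the same, so this is not an effect of a broken table.

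**2. Age of the result at dosing.** The Screening window is Day -8 (+/-6).
- Earliest: -8 - 6 = Day -14
- Latest: -8 + 6 = Day -2
- The SAP puts the Day -1 laboratory draw at Hour -23, so Day -1 is the day before dosing and there is no Day 0.
- Age at dosing: 2 to 14 days, 8 at the nominal visit.

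**3. What a pre-dose draw would change.** Let *a* be the age of the test at dosing and *L* the time from conception until the assay turns positive. Conceptions in the last *a + L* days before dosing go undetected. The documents do not give *L*; take 8 to 12 days as an illustrative assumption.

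| Timing of last pre-dose test | *a* (days) | *a + L* (days) |
|---|---|---|
| Screening, as planned | 2 to 14 | 10 to 26 |
| Day -1 draw (SAP, Hour -23) | about 1 | about 9 to 13 |
| Day 1 draw | 0 | 8 to 12 |

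Only *a* can be reduced. The gain is 1 to 13 days with the Day -1 draw (2 - 1 to 14 - 1), or 2 to 14 days with a Day 1 draw, whatever *L* is.

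**4. What contraception covers.** The requirement starts 28 days before Screening, which is 2 + 28 = 30 to 14 + 28 = 42 days before dosing. For a test of age *a*, contraception starts *a* + 28 days before dosing and the undetected span is *a + L*. The whole span is covered whenever *L* is 28 days or less.

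**5. After the last test.** From Day 43 to Day 76 is 76 - 43 = 33 days. With windows of +/-3 and +/-5, the range is (76 - 5) - (43 + 3) = 25 to (76 + 5) - (43 - 3) = 41 days.

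**The case against.** **Contraception already covers the period.** This is the strongest objection, and most of it stands. Step 4 shows that the required contraception spans the whole undetected interval, so an exposure needs contraceptive failure or undisclosed non-compliance. What it does not do is verify status. Inclusion 5 asks for willingness, and the 28 days before Screening can only be self-reported. The protocol itself tests at Screening and Day 43, so it does not treat contraception alone as enough.

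**The numbers are small.** Sixteen subjects are planned, 12 of them on TRL345, and women of childbearing potential are a subset of unstated size. This limits the priority of the point but does not remove the mismatch between the bar and the schedule.

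**The investigator may test anyway.** True, but nothing on Day 1 requires it, and a fully compliant site can dose on a 14-day-old result.

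Two stronger readings are tempting. A reader might infer that the Day 1 check cannot enforce the bar at all. The documents do not support that: pregnancy is a ground for exclusion in its own right, and the check can act on anything known. A Day 1 assay would not enforce an absolute bar either, since *L* remains. A reader might also infer that late pregnancies are not looked for. But Day 76 has adverse event and overall-status assessments, and Section 7.5 requires every pregnancy during the study to be reported. Detection after Day 43 is passive, not absent.

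**Conclusion.** The point holds in a limited form. No current test supports the Day 1 reconfirmation of exclusion 15, and the only scheduled pre-dose result is 2 to 14 days old at dosing. This follows from the Schedule and its window alone and does not depend on the assumed assay lag. The chance of an exposed pregnancy is small given the contraception requirement and the study size; the documents give no basis for an expected count. The change is still worth making, because the exposure is irreversible, reproductive risk is unstudied and the remedy is cheap.

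The 10-to-26-day span should not be quoted as the size of the problem, because 8 to 12 days of it is an assumed lag that no test removes.

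The absence of a pregnancy test in the 33 nominal days (25 to 41 with windows) after Day 43 is an observation only. In a single-dose study no dosing decision depends on a later test, and no passage requires active testing to Day 76.

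**What to change.** Reconcile the Schedule of Events and Section 6.4.1 with Section 7.5 and exclusion 15. The direct way is to add the serum beta-hCG assay that exclusion 15 already names, for women of childbearing potential, to the existing pre-dose safety draw (Day 1 in the protocol, Day -1 in the SAP). The eligibility reconfirmation already in the plan would then rest on a current result, with no new eligibility rule. The protocol and SAP should give the same day for that draw.

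Cost: an amendment to the Schedule and Section 6.4.1, and one extra assay per woman of childbearing potential on blood already being taken. That is at most 16 assays at planned enrolment, if every subject were in that group and none were replaced. An occasional subject may be excluded late, and very early conceptions would still be missed. No change at Day 76 is required.
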